During Stage 2, the subject and their parents/guardians will again return at 6-month intervals for safety and efficacy evaluations and at 3-month intervals for update of concomitant medications and AE assessment. As in Stage 1, both the subject and their parent/guardian must be present for all 6-month visits, but the parent/guardian may attend a 3-month visit without the subject if necessary. At each study visit, unopened/unused and used study medication materials will be returned, concomitant medications will be updated, AE assessment will be conducted, study medication will be dispensed for the next 3-month study period, and treatment adherence assessment will be

performed. At Month 45, subjects will receive their final study medication kit and return at Month 48 for their final study visit assessments.

Subject or their parent/guardian will be encouraged to record their dosing on a daily basis, starting from the same evening after completing their Month 36 visit till the last visit (Stage 2 of the study) in an electronic patient diary (e-diary). The subject or their parent/guardian will be encouraged to use their cell phone to upload e-diary responses. At Month 36 visit, if subject or their parent/guardian do not have a cell phone or are unwilling to use their cell phone, a device will be provisioned by Medidata and provided to the subject. Once the instillation of the eye drops has been successfully completed, subject or their parent/guardian will log into the application to record dosing of the left eye and the right eye and complete diary submission daily. The diary can be completed between 6:00 PM and 11:45 PM. If the subject or their parent/guardian do **not** complete the e-diary within the allotted time, they will **not** be able to enter the missing data retroactively, as the purpose is to collect information on the actual date the study drops were instilled. Once data is submitted, this information will be automatically entered into the study's Medidata Rave database.

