#### **Study Procedures:**

Office Visits should occur within  $\pm 2$  weeks of the expected visit date.

Screening/Randomization/Baseline Visit (Day 0): Sites should complete screening/randomization/baseline procedures and enroll subjects within 30 days from signing the informed consent.

The clinical site will obtain signed informed consent from the parent or legal guardian of the subject and assent from the subject (as applicable). The subject will then undergo screening evaluations to determine eligibility for the study which will include review of medical/ocular and prior medication history, a urine pregnancy test for female subjects of childbearing potential, heart rate (HR), monocular Best-Corrected Visual Acuity (BCVA) measurement at distance and near, photopic pupil size measurement, slit-lamp examination (SLE) (check for narrow angles), tonometry, dilated fundus examination and cycloplegic autorefraction. Height and weight will also be assessed.

Following confirmation of eligibility, the clinical site will measure axial length and, if possible, crystalline lens thickness. The site will access the IRT, which will assign the subject to 1 of the 3 treatment arms and assign the initial study medication kit to be dispensed to the parent/guardian following instruction on administration.

One (1) drop of the study medication will be administered into each eye QD, at bedtime. Because AEs are to be collected beginning after signing of informed consent/assent, the site will document any events that may be volunteered spontaneously by the subject or parent/guardian that occur before the end of the visit.

If the subject requires initial or new spectacles/contact lenses (applicable if the refraction reveals at least -0.50 D myopic progression and/or if the eye care practitioner deems it clinically necessary to improve vision), the site will provide a refractive prescription and lenses/frames (if needed) or soft contact lenses.

All screening evaluations will serve as baseline measurements.

Stage 1 Telephone Checks – (Months 1, 2, 4.5, 7.5, and 10.5): Sites will contact the subject or their parent/guardian by telephone at the end of Month 1 and Month 2 and then midway between office visits during the initial year of the study to collect information regarding AEs and treatment adherence. Telephone checks can be continued or reinstated at any time during the study to assist with maintaining protocol and treatment adherence.

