## 3.7. Administration of Study Medication

**First Dose of Study Medication:** The subject (or caregiver if the subject is not able to self-administer the medication) will administer 1 full drop of the study medication into each eye from a single unit dose ampule at bedtime the evening of the randomization visit.

Each subsequent evening of dosing, the subject or caregiver will administer one full drop into each eye from a single new ampule and close the eyes gently for 30 seconds. The used ampule will be placed in the provided receptacle for return to the study site.

Subjects and/or their parent/guardian should make every effort not to miss administering doses during the study. Should a subject miss a dose, then the subject should wait until the following evening and then continue with his/her regular dosing schedule. Subject should not administer more than 1 dose to each eye per day.

Subjects or their parent/guardian will return all unopened study medication materials at the next office

This document is confidential.

visit. Site personnel will conduct treatment adherence assessment procedures for the last study period and dispense study medication for the next 3-month study period. At the Month 48 visit, final study drug accountability will be conducted. The Month 48 visit will mark the end of study treatment; no further study medication will be dispensed at this visit.

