### 6.2. Key Definitions

Treatment-emergent adverse events (TEAEs) of Stage 1 are defined as any new or worsening of existing adverse events that occur or worsen between the first dose date of Stage 1 and the last dose date of Stage 1.

TEAEs of Stage 2 are defined as any AE the occurs or worsens between the first dose date of Stage 2 and the last dose date of Stage 2.

First dose date for Stage 1 is defined as the first dose of study medication received after randomization in Stage 1.

First dose date for Stage 2 is defined as the first dose of study medication received after the Stage 1 last dose date and subject is re-randomized.

For subjects who did not receive study medication in a given stage, leave first dose date for that stage as missing. If the first dose date is missing and if the subject is randomized, impute the missing first dose date using the randomization date in the analysis of Time to Change from Baseline in Myopia Progression of -0.75D (see 8.3.7 and 8.3.8).

Baseline for Stage 1 is defined as the last measurement prior to first dose of study medication in Stage 1, If an adverse event starts or non-study medication taken on the day of first dose it will be treated as occurring after treatment started. All other planned measurements are presumed to occur prior to first dose of study medication.

Baseline for Stage 2 will be defined as latest results prior to start of study medication in Stage 2, which occurs the day after the Month 36 visit. The results of the Month 36 visit will act as the baseline for Stage 2.

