### 9.3. Adverse Events

The analysis of AEs will be based on the concept of treatment-emergent AEs (TEAEs). An adverse event is any untoward medical occurrence associated with the use of a drug in humans, whether or not considered drug-related.

Treatment-emergent adverse events (TEAEs) of Stage 1 are defined as any new or worsening of existing adverse events that occur or worsen between start (or increase in intensity on or after the first dose date

This document is confidential.

of Stage 1 treatment on day 1) and the last dose date of Stage 1. TEAEs of Stage 2 are defined as any AE that occurs or worsens between the first dose date of Stage 2 and the last dose date of Stage 2.

The first dose date for Stage 1 is defined as the first dose of study medication received after randomization in Stage 1. The first dose date for Stage 2 is defined as the first dose of study medication received after the Stage 1 last dose date and subject is re-randomized. All adverse events (AEs) will be coded using the MedDRA version 20.1 or higher. The following listings of AEs will be provided by Stage and subjects:

- All AEs,
- Serious adverse events (SAEs) Serious ocular and non-ocular AEs, respectively
- All deaths
- TEAEs (overall, ocular, non-ocular, respectively) leading to study withdrawal
- TEAEs (overall, ocular, non-ocular, respectively) leading to study drug discontinuation
- Severe AEs
- Study drug related AEs
- Study drug related SAEs

Treatment-emergent adverse events will be included in summary tables by treatment received for each stage. Ocular TEAEs will be summarized separately from all other TEAEs. An overall summary table of TEAEs for each stage will be produced for the following categories:

- Any Ocular TEAE
- Severe Ocular TEAEs
- Study drug-related Ocular TEAEs
- Serious Ocular TEAEs
- Study drug-related Serious Ocular TEAEs
- Ocular TEAEs leading to study discontinuation
- Ocular TEAEs leading to death
- Any Non-Ocular TEAE
- Severe Non-Ocular TEAEs
- Study drug-related Non-Ocular TEAEs
- Serious Non-Ocular TEAEs
- Study drug-related Serious Non-Ocular TEAEs
- Non-Ocular TEAEs leading to study discontinuation
- Non-Ocular TEAEs leading to death

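### Adverse events starting on the Month 36 visit day are assigned by date alone: to the newly assigned Stage 2 drug on one stated timing, and possibly to neither stage on the other

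*SAP*

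**What the plan says.** **Same-day conventions.** SAP 6.2 gives two, both in its paragraph on the Stage 1 baseline. For AEs: "If an adverse event starts or non-study medication taken on the day of first dose it will be treated as occurring after treatment started". For scheduled assessments: "All other planned measurements are presumed to occur prior to first dose of study medication". The Stage 2 baseline has its own paragraph, which contains no AE sentence.

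**TEAE windows.** In SAP 6.2 and 9.3 each window runs from the first to the last dose date of the stage, with no days added and no time of day. The Stage 2 wording opens: "TEAEs of Stage 2 are defined as any AE that occurs or worsens between the first dose date of Stage 2". TEAE tables group children by the treatment received in that stage.

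**Time of dosing.** The first Stage 1 dose goes "into each eye from a single unit dose ampule at bedtime the evening of the randomization visit" (SAP 3.7). Bedtime dosing continues in Stage 2.

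**Start of Stage 2.** The documents do not agree:
- Protocol synopsis, e-diary text (repeated under the Month 36 visit): doses are recorded "starting from the same evening after completing their Month 36 visit".
- SAP 9.2: the dosing diary starts on the Month 36 visit day.
- SAP 6.2: Stage 2 medication starts on a date "which occurs the day after the Month 36 visit".
- SAP 3.8: Stage 2 begins during the Month 36 visit.
- SAP 6.4: Stage 1 ends once that visit is completed, and Stage 2 begins on the day of the first dose after re-randomisation.

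**Re-randomisation.** Under SAP 3.6.2, Stage 1 Vehicle children are split 1:1 between the two atropine concentrations. Each Stage 1 atropine group is split 1:1:1 over all three treatments.

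**Baseline visit.** The protocol's Study Procedures text reads "Because AEs are to be collected beginning after signing of informed consent/assent", and sites are to "document any events that may be volunteered spontaneously by the subject or parent/guardian that occur before the end of the visit".

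**The concern.** At the Month 36 visit a child is examined, has an AE assessment and receives the Stage 2 kit. The first Stage 2 drop comes at bedtime at the earliest. An AE that starts on that day will usually have started after three years on the Stage 1 drug and before any exposure to the next one. A window that compares dates only cannot see this order.

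The drug changes that follow are fixed by design. Re-randomised Vehicle children can only receive atropine, and the Stage 2 Vehicle arm consists only of former atropine children. A visit-day event credited to the wrong drug would therefore move from Vehicle to atropine, or from atropine to Vehicle, in the TEAE tables. Safety over three years is part of the primary objective, so the Stage 1 tables should not lose events that began under the Stage 1 drug.

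**Working it through.** The plan gives no figure for this rule, so the check is one of date logic, followed by a count of the children whose drug changes.

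**Step 1. Classify an AE with onset on the Month 36 visit day.** Call the visit day 0. The AE is in Stage 1 if 0 ≤ last Stage 1 dose date, and in Stage 2 if 0 ≥ first Stage 2 dose date.

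| Timing | Last Stage 1 dose | First Stage 2 dose | Result |
|---|---|---|---|
| (a) Protocol and SAP 9.2; last Stage 1 dose the evening before | −1 | 0 | Stage 2 TEAE, new drug |
| (b) SAP 6.2; last Stage 1 dose the evening before | −1 | +1 | Neither stage |
| (c) SAP 6.2; a Stage 1 dose taken on the visit evening | 0 | +1 | Stage 1 TEAE |

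The −1 in (a) and (b) is an inference. It rests on bedtime dosing and on Stage 1 materials being returned at the visit (protocol Schedule of Procedures). The SAP does not define the last Stage 1 dose date further. Case (c) needs a Stage 1 dose on the visit evening, which sits poorly with the return of materials and the dispensing of the Stage 2 kit.

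Result (a) does not depend on the same-day sentence in SAP 6.2. The Stage 2 window alone produces it, because the onset date equals the first dose date.

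**Step 2. Change of drug under (a), among re-randomised children.**
- Vehicle, 1:1: 0 stay on Vehicle and 100% go to atropine.
- 0.02%, 1:1:1: 1/3 stay, 1/3 go to 0.01% and 1/3 to Vehicle. So 2/3 change arm, half of these to Vehicle.
- 0.01%, 1:1:1: 2/3 change arm in the same way.

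**Step 3. Children at planned numbers.** The inputs are 138, 138 and 207 randomised (Vehicle, 0.01%, 0.02%) and 27% Stage 1 drop-out, from the protocol's Number of Subjects text. I assume equal drop-out by arm and that every completer is re-randomised.
- Reading check on the inputs: 207 × 0.73 = 151.1, in line with the protocol's statement of at least 150 on 0.02%.
- Vehicle: 138 × 0.73 = 100.7, or about 50 to each concentration.
- Total re-randomised: 100.7 + 100.7 + 151.1 = 352.6 (unrounded values).
- Changing drug: 100.7 + (2/3 × 100.7) + (2/3 × 151.1) = 268.6, and 268.6 / 352.6 = 76%.

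These are children for whom a visit-day AE would be credited to a different drug. They are not numbers of AEs.

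**Step 4. Share of examinations.** Month 36 is one of six post-baseline Stage 1 slit-lamp and pressure examinations (1/6 = 17%) and one of three fundus examinations (1/3 = 33%). These are shares of the schedule. They would be shares of AEs only if examination AEs were dated to the examination and spread evenly, which the documents do not say.

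**Step 5. Consistency within the SAP.** Month 36 results form the Stage 2 baseline, and SAP 6.4 places the completed visit in Stage 1. Under (a), one abnormality first noted that day could be a Stage 2 baseline value in one table and a Stage 2 TEAE in another.

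**The case against.** The strongest reply is that SAP 6.2 itself starts Stage 2 medication on the following day. On that text nothing dated to the visit is charged to the next drug. This stands, so the wrong-drug result holds only on the timing in the protocol and SAP 9.2. It does not rescue the plan, because on the SAP 6.2 timing the event may be in no TEAE table at all.

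A reader might go further and say that on either timing the event is never counted under the Stage 1 drug. The documents do not establish that. Case (c) gives Stage 1. SAP 9.1 also substitutes the last clinic visit when the last dose date is unknown; carried into the TEAE window with a next-day Stage 2 start, that would give Stage 1 as well. SAP 9.1 states this for exposure only.

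A reader might also infer that Month 36 examination findings go to the wrong arm. They do not: SAP 9.7 to 9.9 tabulate slit-lamp, fundus and pressure results by stage, visit and treatment. Only a separately recorded AE with onset that day is affected, and an event found at the visit but dated earlier stays in Stage 1. Nor is every Vehicle child concerned, since children off medication do not enter Stage 2.

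At baseline, AEs with onset on the randomisation day before the bedtime dose do count as Stage 1 TEAEs. This is an inclusive convention that falls equally on all arms. It does not bias the difference between them, and is a minor point.

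Finally, Stage 2 is exploratory, AE output is descriptive, and outputs covering both stages use the treatment sequence, which shows the earlier drug. That lowers the stakes but leaves the by-stage TEAE tables with an unsettled rule.

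**Conclusion.** The point holds for AEs whose recorded onset is the Month 36 visit day. On the protocol and SAP 9.2 timing they are credited to a drug that the child has normally not yet taken: always atropine for re-randomised Vehicle children, and a different arm for two-thirds of re-randomised 0.02% children. On the SAP 6.2 timing they fall in neither stage, provided that the last Stage 1 dose was the evening before.

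The number of such AEs is unknown and could be close to zero. The documents give no rate, and the supplied text does not say how sites date the onset of events noticed at an examination. The 17% and 33% must not be read as shares of AEs. The case for change is that the plan contradicts itself on a date that decides drug attribution, and that a simple default rule settles it.

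**What to change.** In SAP 6.2 and 9.3, state that an AE with onset on the Month 36 visit date is a Stage 1 TEAE under the Stage 1 drug, unless the record shows onset after the first Stage 2 dose. Reconcile the Stage 2 start wording in SAP 3.8, 6.2 and 6.4 with SAP 9.2 and the protocol's e-diary and Month 36 visit text. This review takes no view on which dosing start is right.

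The cost is a wording change and one derivation rule. The default needs only the onset date and the visit date, both already collected. The exception needs evidence that onset followed the dose, and the documents do not show that AE onset time is recorded. The downside is that a rare event starting late that night, with no recorded time, would stay in Stage 1.

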### 6.3. Missing Data

Partial dates of medications will be imputed solely for the purpose of defining prior/concomitant status for medications and treatment emergence for adverse events. Dates will be defined using the hierarchy of derivations below.

This document is confidential.

- For missing start day where month and year are present, the start day will be set to the 1st of the month, unless the month and year are the same as the first dose month and year and the 1st of the month is before the first dose date, in which case, the start date will be set to the first dose date.
- For missing start day and month where year is present, the start day and month will be set to January 1st, unless the year is the same as the first dose year and January 1st is before the first dose date, in which case, the start date will be set to the first dose date.
- For missing end day where month and year are present, the end day will be set to the last day of the month, unless the month and year are the same as the subject study termination month and year, in which case, the end date will be set to the trial termination date.
- For missing end day and month, where year is present, the end date will be set to the trial termination date if the years are the same. If the trial termination year is greater than the end year, the end day and month will be set to December 31st.

Missing efficacy data will be addressed in the related subsection of 8 below.

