#### 7.5.2. Concomitant Medication

Concomitant medications are defined as medication on the eCRF that are taken on or after or are ongoing at the start date of dosing for each stage. Concomitant medications will be summarized by ATC level 2 and preferred drug name for the Safety Set for each stage.

This document is confidential.

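### SAP 6.3 moves partial start dates to the first dose date with no end-date check and no stage named, so some resolved adverse events can become treatment-emergent and switch-month events have no defined stage

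*SAP*

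**What the plan says.** SAP 6.3 imputes partial dates "solely for the purpose of defining prior/concomitant status for medications and treatment emergence for adverse events". When only the day of a start is missing, the default is day 1 of that month. The exception begins "unless the month and year are the same as the first dose month and year and the 1st of the month is before the first"; when it applies, the start becomes the date of first dosing. A start with missing day and month goes to January 1st, "unless the year is the same as the first dose year and January 1st is before the first dose date", with the same consequence. End dates are imputed in separate bullets. Nothing in the section requires a start to precede its end.

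SAP 6.2 defines a first dose date for each stage: "First dose date for Stage 2 is defined as the first dose of study medication received after the Stage 1 last dose date" and after re-randomization. Treatment-emergent events are also defined by stage. In Stage 1 they must "occur or worsen between the first dose date of Stage 1 and the last dose date of Stage 1"; in Stage 2 they are "any AE the occurs or worsens between the first dose date of Stage 2 and the last dose date of Stage 2". An event that starts "on the day of first dose it will be treated as occurring after treatment started". SAP 9.3 tabulates these events by the treatment received in each stage.

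For medications, SAP 7.5.1 classes a record as prior if either its start or its end precedes the first dose. SAP 7.5.2 adds: "Concomitant medications are defined as medication on the eCRF that are taken on or after or are ongoing at the start date of dosing", applied to each stage.

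**The concern.** The start-date rule can override information that the eCRF already holds. If the end date shows that an event was over before dosing, moving its start to the first dose date produces a record that begins after it ended, and 6.2 then counts it as on-treatment.

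The rule also refers to first dose as if there were only one. At Month 36 there are two candidate dates, and the choice decides whether a partial-date event falls in Stage 1 or Stage 2. For a child randomized to Vehicle in Stage 1 this is a choice between Vehicle and atropine, because SAP 3.6.2 re-randomizes those children only to active treatment. If the study's first dose is meant, nearly every unknown-day event in such a child's switch month is filed under Vehicle, even if it followed the first atropine drop. Two programmers could follow the SAP correctly and produce different stage-specific safety tables.

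**Working it through.** The documents state no figure for this rule, so there is none to reproduce. The check applies the rules of 6.3 and 6.2 to assumed dates: Stage 1 first dose 15 Jun 2018, Stage 1 last dose 14 Jun 2021, Stage 2 first dose 15 Jun 2021.

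1. **Adverse event resolved before first dose.** Start recorded as Jun 2018, end 5 Jun 2018. The month matches and 1 Jun precedes 15 Jun, so the start becomes 15 Jun 2018. That is 15 − 5 = 10 days after the end. Under 6.2 it is a Stage 1 treatment-emergent event.

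2. **Medication ended before first dose.** Start recorded as 2018, end 10 Mar 2018. The start becomes 15 Jun 2018, which is 21 + 30 + 31 + 15 = 97 days after the end. The end date keeps it prior under 7.5.1. It is concomitant as well only if 7.5.2 is programmed on the imputed start.

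3. **Event in the switch month or year.**
   - Recorded as Jun 2021: 1 Jun 2021 (Stage 1) if first dose means Stage 1; 15 Jun 2021 (Stage 2) if it means Stage 2.
   - Recorded as 2021: 1 Jan 2021 (Stage 1) or 15 Jun 2021 (Stage 2).
   - Under the Stage 2 choice, a Jun 2021 event with a recorded end of 5 Jun also becomes a Stage 2 event that starts after its end.

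4. **Share misplaced.** Assume the true onset is uniform over the N days of the recorded month or year, with the switch on day d > 1. The Stage 1 choice is wrong for N − d + 1 days and the Stage 2 choice for d − 1 days.
   - Month known, N = 30, d = 15: 16 of 30 and 14 of 30.
   - Year only, N = 365, switch 15 Jun: 200 of 365 and 165 of 365.
   - If d = 1, both choices give Stage 2 and neither errs.
   - Averaged over d, each choice misplaces (N − 1)/(2N): 29/60 = 48% for a 30-day month and 364/730 = 50% for a year. Running the rule over all 365 switch dates with actual month lengths gives 48.4% and 49.9%.

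5. **Who is exposed.** From the Protocol Synopsis: 138, 138 and 207 per arm and 27% Stage 1 drop-out, so a factor of 0.73.
   - All Stage 2 entrants: 483 × 0.73 ≈ 353.
   - Formerly on Vehicle: 138 × 0.73 ≈ 101, all of whom change treatment.
   - Formerly on active: 345 × 0.73 ≈ 252. With 1:1:1 re-randomization about two thirds (168) change treatment, and one third (84) go to Vehicle.

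6. **Illustrative count.** The event rate and partial-date share are assumptions, not document figures: 0.1 to 0.2 events per child-month, 5% to 10% with unknown day.
   - All entrants: 353 × 0.1 × 0.05 = 1.8 to 353 × 0.2 × 0.10 = 7.1 events; about half, 0.9 to 3.5, misplaced.
   - Formerly on Vehicle: 101 × 0.1 × 0.05 = 0.5 to 101 × 0.2 × 0.10 = 2.0 events; about half, 0.25 to 1.0, misplaced.

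**The case against.** Four points limit this.

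- **Medications.** A reader might infer that medications finished before dosing must appear as concomitant. The definitions do not support that: 7.5.1 classes them as prior by their end date and adds concomitant status only when use continues past first dose, and a literal reading of 7.5.2 excludes them. What stands is that a program working from the imputed start alone would let them in, and 6.3 does not prevent it.
- **Pre-dose events.** The Protocol Synopsis collects adverse events from consent and has subjects enrolled within 30 days of it, and SAP 3.7 places the first dose on the evening of randomization. Only events that began and ended in that gap, with an unknown start day, are exposed. Moving an uncertain start to first dose is otherwise conservative.
- **Stage.** A reader might infer that switch-month events are always charged to the wrong stage. They are not: the stage is undefined, and each choice is right for about half of them. An unknown onset day carries that uncertainty under any rule. Year-only onsets are also implausible for adverse events assessed every three months.
- **Visibility.** SAP 13.2.5.3 shows missing date parts as dashes in listings, and all adverse events are listed, so each affected record can be found.

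All four stand as limits on size. None supplies the missing end-date condition or names the stage.

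**Conclusion.** The point holds as a minor defect. Followed literally, 6.3 and 6.2 turn an adverse event that resolved before dosing into a Stage 1 treatment-emergent event with its start after its end. For partial-date events in the switch month the stage is not defined. Under uniform onset, either choice of first dose date misplaces about 48% of events with an unknown day and 50% of those with only a year. If the study's first dose is used, the errors all run towards Stage 1.

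The number affected is unknown, because the documents give no count of partial dates. The illustrative range of about 1 to 4 misplaced events among all entrants, and at most about 1 among children formerly on Vehicle, rests on assumed rates. The effect is confined to the stage-specific adverse event tables and, possibly, the concomitant medication tables. No efficacy test is affected.

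**What to change.** Add two sentences to SAP 6.3:

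1. A partial start is shifted to the first dose date only if the end date is missing, ongoing, or on or after that first dose; an imputed start may never be later than the recorded end.
2. The rule applies by stage. A partial adverse event start that could fall on or after the Stage 2 first dose, and whose end is not before it, is set to the Stage 2 first dose date; otherwise the event stays in Stage 1.

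The cost is a few lines of derivation code and no new data. It is best settled before the Stage 1 analysis, after which SAP 11 allows study personnel other than investigators, site staff and CRAs to be unblinded for Stage 1.

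The rule makes allocation reproducible but cannot recover the true day. Where the end date does not settle the matter, it errs as the Stage 2 choice does (14 of 30 days in the example), so some Stage 1 events will be assigned to the newly started treatment. That is the conservative direction for children starting atropine. For the roughly 84 formerly active children re-randomized to Vehicle it files such events under Vehicle, so the tables should carry a footnote stating the rule and the number of events it placed.
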